10.1.5. Laboratory Test Abnormalities

Abnormal laboratory findings (eg, chemistry, hematology, coagulation) or other abnormal assessments (ECGs, X-rays, vital signs) that are judged by the investigator as clinically significant will be recorded as AEs or SAEs. This includes clinically significant abnormal laboratory findings or other abnormal assessments that are present at baseline and significantly worsen during the study. The definition of clinically significant is left to the judgement of the investigator; in general, these

are the abnormalities that are associated with clinical signs or symptoms, require active medical intervention, or lead to dose interruption or discontinuation, or require close observation, or more frequent follow-up assessments, or further diagnostic investigation.

10.2. Definition of a Serious Adverse Event

An SAE is any untoward medical occurrence that, at any dose:

- Results in death.
- Is life-threatening.

NOTE: The term “life-threatening” in the definition of “serious” refers to an AE in which the patient was at risk of death at the time of the AE. It does not refer to an AE, which hypothetically might have caused death, if it were more severe.

- Requires hospitalization or prolongation of existing hospitalization.

NOTE: In general, hospitalization signifies that the patient was admitted (usually involving at least an overnight stay) to the hospital or emergency ward for observation and/or treatment that would not have been appropriate in the physician’s office or outpatient setting. Complications that occur during hospitalization are AEs. If a complication prolongs hospitalization or fulfills any other serious criteria, the AE is serious. When in doubt as to whether “hospitalization” occurred or was necessary, the AE should be considered serious.

- o Hospitalization for elective treatment of a pre-existing condition that did not worsen from baseline is not considered an SAE.
 - o Hospitalization for social/convenience considerations is not considered an SAE.
 - o Scheduled therapy for the target disease of the study, including admissions for transfusion support or convenience, is not considered an SAE.
- Results in disability/incapacity.

NOTE: The term disability means a substantial disruption of a person’s ability to conduct normal life functions. This definition is not intended to include experiences of relatively minor medical significance, such as uncomplicated headache, nausea, vomiting, diarrhea, influenza, and accidental trauma (eg, sprained ankle), which may interfere or prevent everyday life functions, but do not constitute a substantial disruption.

- Is a congenital anomaly/birth defect.
- Is considered a significant medical AE by the investigator based on medical judgement (eg, may jeopardize the patient or may require medical/surgical intervention to prevent one of the outcomes listed above).

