1.2.4. Treatment Toxicity

The dose-limiting factor associated with chemotherapy for GBM is bone marrow toxicity. Daily, low-dose TMZ given concomitantly with RT rarely affects platelet or neutrophil counts, but patients usually experience some degree of lymphopenia. In contrast, the standard TMZ dosing and schedule (Stupp et al 2005) used for adjuvant treatment frequently causes neutropenia and/or thrombocytopenia.

To achieve clinical benefit, it is imperative that the magnitude of any sensitizing effect for TMZ is significantly greater in the tumor than in the critical normal tissues. Targeting DNA repair pathways might be predicted to achieve tumor-specific chemo- and/or radio-sensitization.

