1.2.4.1. Toxicity of Dose-dense Temozolomide Regimens

Studies have been conducted to assess the safety concerns (Neyns et al 2010). The greater dose intensity achieved in these studies does not appear to significantly increase the frequency of

thrombocytopenia or neutropenia (Gilbert et al 2013). Available data from Phase 2 trials indicate a high incidence of lymphopenia (8% to 68%), a common TMZ toxicity, and a slight increase in fatigue. Grade 3 or 4 lymphopenia in trials using the 21 of 28 days TMZ schedule (75 mg/m²) occurred in 24% to 53% of cases, and Grade 4 lymphopenia, which may increase the risk of opportunistic infections, was reported in 47% in one study for recurrent anaplastic astrocytoma or oligoastrocytoma (Neyns et al 2008).

In the RTOG 0525 study, adverse events (AEs) were evaluated separately during the concurrent chemo- and radiotherapy and the adjuvant treatment phase. Grade 3 or 4 lymphopenia was the most common toxicity occurring in 12% of patients but without significant opportunistic infections. Serious neutropenia and thrombocytopenia occurred in 3.6% and 6.8%, respectively, of all patients undergoing RT. There was one treatment-related death as a result of neutropenia (Gilbert et al 2013).

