Several clinical studies have been conducted with PARP inhibitors (olaparib, rucaparib, and veliparib) in combination with TMZ. To determine the maximum tolerated dose (MTD) in these studies, TMZ was administered at standard doses (135 to 150 mg/m²/day or up to 1000 mg/m²/month) with increasing doses of the PARP inhibitor. All studies experienced the challenge of significant myelosuppression as dose-limiting toxicities (DLTs), and observed anti-tumor activity was only modest (Gabrielson et al 2015; Gojo et al 2017; Hussain et al 2014; Middleton et al 2015; Plummer et al 2013; Su et al 2014). This is contrasted by a recent study for talazoparib, a PARP inhibitor with very good DNA-trapping activity. Standard doses of talazoparib (0.5 to 1 mg) were administered with low doses of TMZ in patients with non-*BRC1/2*-mutated cancers (Wainberg et al 2016) The starting dose of TMZ was 25 mg/m², approximately 12.5% of the therapeutic dose, and the MTD was determined as 1 mg talazoparib plus 37 mg/m² of TMZ. This regimen was better tolerated than reported for prior studies, with less thrombocytopenia and neutropenia. Furthermore, promising efficacy was observed with 11 patients (61%) experiencing either a partial response or stable disease. These preliminary clinical results are in support of the hypothesis that PARP inhibitors with strong DNA-trapping activity may only require relatively low TMZ dose levels to exert their anti-tumor activity.

Ionizing radiation used in the clinical treatment of GBM generates mostly SSBs and to a minor extent DSBs. Single-strand breaks are repaired through the BER pathway, operating via either the *short patch* or the *long patch* repair sub-pathways, which differ in the size of the repair patch and the enzymes involved. A PARP-1 role in the *short patch* is well established, but its contribution in the *long patch* is still unclear. In non-replicating cells, PARP inhibition only delays the repair of SSBs

induced by radiation with a minimal impact on cell survival. On the contrary, PARP inhibition markedly enhances radiosensitivity of proliferating cells since unrepaired SSBs collide with the DNA replication machinery, generating DSBs. Thus, PARP inhibitors have the potential to increase the anti-tumor effect of RT by preventing DNA damage repair and increasing cytotoxic DNA damage (Godon et al 2008; Noel et al 2006; Dungey et al 2008).

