1.3.5.2. Exploratory Biomarker Data

1.3.5.3. Clinical Safety and Preliminary Efficacy for BGB-290-AU-002

BGB-290-AU-002 is a first-in-human trial evaluating pamiparib to characterize the safety, the MTD, preliminary anti-tumor activity and the pharmacokinetics of pamiparib given as a monotherapy in a 3+3 dose escalation scheme. Pamiparib was administered in doses ranging from 2.5 mg PO BID up to 120 mg PO BID.

The study is being conducted in 5 Australian study centers, and preliminary data for 45 patients are available (cutoff date of 30 September 2016).

The preliminary safety data indicate that the most frequent adverse events (AEs) ($\geq 10\%$ of patients) assessed as related to pamiparib were nausea (58%, n = 26), vomiting (51%, n = 23), fatigue (29%, n = 13), diarrhea (18%, n = 8), dry mouth (16%, n = 7) and decreased appetite (11%, n = 5).

Hematologic AEs are of interest in this study. The most frequent hematologic AEs ($\geq 10\%$ of patients) assessed as related to pamiparib were anemia (22%, n = 10) and neutropenia (11%, n = 5).

Hematologic AEs, regardless of relatedness, were reported in 40% of patients (n = 18). Anemia was most frequent (33%, n = 15), followed by neutropenia (11%, n = 5) and thrombocytopenia (2%, n = 1).

Twenty-six patients experienced Grade 3 AEs (regardless of relatedness), and no Grade 4 AEs were reported. Eleven Grade 3 AEs in 9 patients (20%) were considered related to pamiparib: anemia (n = 5), neutropenia (n = 3), hypophosphatemia (n = 1), nausea (n = 1) and fatigue (n = 1). Serious AEs (SAEs) reported as related to pamiparib included anemia (n = 2) and nausea (n = 1).

SAEs were reported in 25 patients, and for 3 patients they were considered related to BGB 290: anemia (n = 2) and nausea (n = 1). Three patients discontinued study drug because of an AE: vomiting (n = 1), oral paresthesia (n = 1), and right neck cutaneous metastases (n = 1).

Four patients experienced a fatal AE \leq 28 days after the last pamiparib dose. All deaths were due to complications of the underlying malignancy, and none was considered related to pamiparib.

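### The SAE definition names admission for transfusion as exempt target-disease therapy, which does not fit glioblastoma and can keep transfusion-only admissions for new cytopenia out of SAE counts and 24-hour reporting

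*Protocol*

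**What the plan says.** Protocol 10.2 lists the seriousness criteria. One is: "Requires hospitalization or prolongation of existing hospitalization." Three exemptions follow under that criterion. The first two cover elective treatment of a pre-existing condition that has not worsened since baseline, and social or convenience admissions. The third reads: "Scheduled therapy for the target disease of the study, including admissions for transfusion support or convenience, is not considered an SAE."

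The same section keeps other routes to seriousness. For events during a stay: "If a complication prolongs hospitalization or fulfills any other serious criteria, the AE is serious." An event also counts if it "Is considered a significant medical AE by the investigator based on medical judgement". Doubt over whether a hospitalization took place or was needed is settled as serious.

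Protocol 7.2.1 lists red cell and platelet transfusion with permitted supportive care. Study treatment is pamiparib, RT and TMZ (Protocol 11.2.1). Transfusion is in none of the Appendix 1 schedules.

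**The concern.** The exemption is written for scheduled treatment of the disease under study. In glioblastoma no transfusion is scheduled, so the example has no evident use. Its most likely practical effect is on patients admitted because hemoglobin or platelets have fallen on study.

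That matters because the protocol expects marrow toxicity. Section 1.2.4 states: "The dose-limiting factor associated with chemotherapy for GBM is bone marrow toxicity." Section 1.3.3 reports that myelosuppression was dose-limiting in the listed studies of olaparib, rucaparib and veliparib with TMZ.

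Two things depend on SAE status. SAEs and treatment-related SAEs are tabulated (Protocol 11.3.3, SAP 6.5.3). An SAE must also reach the sponsor within 24 hours (Protocol 10.5.1) and is then assessed for expedited reporting (Protocol 10.5.3 and 10.8). If some sites follow the example and others follow the hospitalization criterion, the same event is counted differently by site.

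**Working it through.** The plan gives no figure to reproduce. The check is mainly of the text, with simple proportions for scale.

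**1. Two readings of the clause.**
- *By its opening words.* Only scheduled therapy for glioblastoma is exempt. Transfusion is not such a therapy, so an unplanned admission for drug-related anemia stays serious, and the transfusion example covers nothing.
- *By its example.* Any admission for transfusion support is exempt, which contradicts the hospitalization criterion.

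The text does not settle which applies. The rule on doubt concerns whether a hospitalization occurred or was necessary. It does not address whether an exemption applies.

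**2. What the example adds to the neighboring exemptions.** Eligibility foresees transfusion before study entry (Protocol 5.1, hemoglobin criterion). An elective admission for a stable baseline need is already covered by the first exemption, and convenience by the second. What remains is mainly new or worsened cytopenia, or blood loss.

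**3. Whether other routes pick up the omitted events** (admission for transfusion with no other seriousness criterion met).
- *DLTs (Protocol 4.2.4).* Anemia counts only at Grade 4 or above. Grade 3 thrombocytopenia counts only with clinically significant bleeding. Grade 3 anemia (hemoglobin below 8 g/dL in Protocol Table 4) admitted for transfusion is therefore not a DLT.
- *DLT window.* It is 28 days in Arm C (Protocol 4.2.3), and the SAP restricts the DLT set to escalation patients (SAP 6.1). Later Arm C cycles, maintenance and expansion have no DLT count.
- *AE, Grade 3 or higher, dose-modification and laboratory-grade tables* (SAP 6.5.3 and 6.5.4). The cytopenia appears there, but those tables do not trigger the 24-hour report.
- *Medically significant criterion.* It remains open, but it depends on the investigator's judgement.

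**4. Scale, from the monotherapy study** (Protocol 1.3.5.3, 45 patients; exact 95% confidence intervals).
- Related anemia: 10/45 = 22.2% (11.2 to 37.1). Related neutropenia: 5/45 = 11.1% (3.7 to 24.1). Both agree with the protocol's rounded figures.
- Related SAEs: 3 patients, two with anemia and one with nausea. 3/45 = 6.7% (1.4 to 18.3).
- The documents do not say why the two anemia cases were serious, so the range is:

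| Anemia SAEs that were transfusion-only admissions | Related-SAE rate under the example |
|---|---|
| 0 of 2 | 3/45 = 6.7% |
| 1 of 2 | 2/45 = 4.4% |
| 2 of 2 | 1/45 = 2.2% (0.1 to 11.8) |

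That study reported no Grade 4 AEs and no related deaths. The two anemia cases were therefore probably serious through hospitalization or medical judgement, but which of these is not stated.
- Of 11 related Grade 3 AEs, 5 were anemia and 3 neutropenia: 8/11 = 73%. None of these would leave a Grade 3 or higher table under either reading.

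**The case against.** The strongest reply is that the clause is qualified. It exempts scheduled therapy for the target disease, and the transfusion phrase is subordinate to that. Read strictly, it removes nothing that matters here. This stands to the extent that the defect is ambiguity and not a clear blanket exemption. It does not remove the problem, because the strict reading leaves the example with no content and a site may reasonably follow the example it is given.

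Second, other seriousness routes remain: death, life-threatening events, prolonged stays and medically significant events. Section 10.2 also ties hospitalization to care that would not suit an outpatient setting, so some transfusion admissions may not qualify in any case. This stands, and it confines the gap to admissions that meet the hospitalization criterion alone.

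Third, escalation decisions rest on DLTs and on review of AEs and laboratory data (Protocol 4.2.2), not on SAE counts. Hematology is weekly in Arm C Cycle 1 and during RT. This also stands. A reader might infer that escalation goes unmonitored for marrow toxicity, and the documents do not support that.

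Fourth, a reader might infer that SAE counts miss the main expected toxicity. They do not. In the dose-dense TMZ trial cited in Protocol 1.2.4.1, "Grade 3 or 4 lymphopenia was the most common toxicity occurring in 12% of patients but without significant opportunistic infections". Neither lymphopenia nor neutropenia leads to a transfusion-only admission, and a bleed that needs admission is an SAE in its own right.

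**Conclusion.** The point holds as a wording conflict with a bounded consequence. The transfusion example does not fit glioblastoma, contradicts the hospitalization criterion, and can leave transfusion-only admissions for treatment-emergent anemia or thrombocytopenia out of SAE counts and 24-hour reporting. It is worth correcting because the SAE tables are a planned output and the SAP has no step to reconcile classification across sites.

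The size of the effect is unknown. The monotherapy data give a range from no change (6.7%) to a fall to 2.2%, a difference of at most 2/45 = 4.4 percentage points. This assumes that the clause would have applied in that study, whose SAE definition is not given, and it rests on two patients. Quoting only the lower end as a two-thirds reduction would go beyond the evidence.

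Two further inferences are not supported. One is that every transfusion admission here must be treatment-caused: no passage limits the causes, and eligibility foresees transfusion before treatment. The other is that the effect must be larger than in monotherapy. Protocol 1.5 does anticipate that AEs may be more frequent or severe with the combinations, but Protocol 1.3.3 also cites a study of a strongly trapping PARP inhibitor with low-dose TMZ that was better tolerated, with less thrombocytopenia and neutropenia than prior studies.

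**What to change.** In Protocol 10.2, delete the reference to transfusion support from the exemption, or limit it to planned admissions for a condition present at baseline that has not worsened. Either change brings the clause into line with the hospitalization criterion. Carry the same wording into the SAE reporting instructions given to sites.

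The SAP reports enrollment as 116 patients (46 + 40 + 30, SAP section 5), so a change of wording alone may reach few events. Before the SAE tables are run, query admissions linked to anemia or thrombocytopenia AEs, classify them by one rule across sites, and state that rule in SAP 6.5.3. Send any event newly classified as serious through the usual SAE report.

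The cost is one sentence, a limited data query and a possibly higher reported SAE count.

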10.3. Timing, Frequency, and Method of Capturing Adverse Events and Serious Adverse Events

10.3.1. Adverse Event Reporting Period

After the ICF has been signed but before study treatment, only SAEs should be reported, as required per [Section 10.5](#).

After initiation of study treatment, all AEs and SAEs, regardless of relationship to study treatment, will be reported until 30 days after the last study treatment or initiation of new anticancer therapy, whichever occurs first. After this period, the investigator should report any SAEs that are believed to be related to prior study treatment.

10.3.2. Eliciting Adverse Events

The investigator or designee will ask about AEs by asking the following standard questions:

- How are you feeling?
- Have you had any medical problems since your last visit?
- Have you taken any new medicines since your last visit?

10.4. Specific Instructions for Recording Adverse Events and Serious Adverse Events

10.4.1. Disease Progression

Disease progression and death due to disease progression, which is expected in this study population and measured as an efficacy endpoint, should not be reported as an event term. Instead, the symptoms, signs or clinical sequelae that result from disease progression should be reported as the events.

For instance, a patient presents with pleural effusion resulting from disease progression of metastasis to lungs. The event term should be reported as “pleural effusion” instead of disease progression. If a patient experienced a fatal multi-organ failure due to disease progression, the term “multi-organ failure” should be reported as the SAE with death as outcome instead of reporting “fatal disease progression” or “death due to disease progression”.

10.4.2. Death

Death is an outcome and not usually considered an AE. If the only information available is death and the cause of death is unknown, then the death is reported as an event, eg “death”, “death of unknown cause”, or “death unexplained”.

10.5. Prompt Reporting of Serious Adverse Events

10.5.1. Timeframes for Submitting Serious Adverse Events

As soon as the investigator determines that the AE meets the protocol definition of an SAE, the event must be reported promptly (within 24 hours) to the sponsor or designee as described in [Table 5](#).

Table 5: Timeframes and Documentation Methods for Reporting Serious Adverse Events to the Sponsor or Designee

	Timeframe for Making Initial Report	Documentation Method	Timeframe for Making Follow-up Report	Documentation Method	Reporting Method
All SAEs	Within 24 hours of first knowledge of the AE	SAE Report	As expeditiously as possible	SAE Report	Email or fax SAE form or Pregnancy form

Abbreviations: AE, adverse event; SAE, serious adverse event.

10.5.2. Completion and Transmission of the Serious Adverse Event Report

Once an investigator becomes aware that an SAE has occurred in a patient, he/she is to report the information to the sponsor within 24 hours as outlined above in [Section 10.5.1](#). The SAE Report will always be completed as thoroughly as possible with all available details of the event, and forwarded to the sponsor or designee within the designated time frames.

If the investigator does not have all information regarding an SAE, he/she is not to wait to receive additional information before notifying the sponsor or designee of the SAE and completing the form. The form will be updated when additional information is received.

The investigator must always provide an assessment of causality at the time of the initial report as described in [Section 10.1.1](#).

The sponsor will provide contact information for SAE receipt.

10.5.3. Regulatory Reporting Requirements for Serious Adverse Events

The investigator will promptly report all SAEs to the sponsor in accordance with the procedures detailed in [Section 10.5.2](#). The sponsor has a legal responsibility to notify, as appropriate, both the local regulatory authority and other regulatory agencies about the safety of a product under clinical investigation. Prompt notification of SAEs by the investigator to the appropriate project contact for SAE receipt is essential so that legal obligations and ethical responsibilities towards the safety of other patients are met.

The investigator, or responsible person according to local requirements, will comply with the applicable local regulatory requirements related to the reporting of SAEs to regulatory authorities and the IRB/IEC.

This protocol is being filed under an Investigational New Drug (IND) protocol amendment with the United States Food and Drug Administration (FDA). Once active, a given SAE may qualify as an IND safety report if the SAE is both attributable to the study drug and unexpected. In this case, all investigators filed to the IND (and associated INDs for the same compound) will receive an expedited investigator safety report, identical in content to the IND safety report submitted to the FDA.

Expedited investigator safety reports are prepared according to the sponsor's policy and are forwarded to investigators as necessary. The purpose of the report is to fulfill specific regulatory and GCP requirements regarding the product under investigation.

When a study center receives an initial or follow-up report or other safety information (eg, revised IB) from the sponsor, the responsible person according to local requirements is required to promptly notify his/her IRB or IEC.

Expedited Reporting of Suspected Unexpected Serious Adverse Reactions (SUSARs)

BeiGene, as study sponsor, is responsible for reporting suspected, unexpected, serious adverse reactions involving the study drug to all regulatory authorities and participating investigators in accordance with International Council for Harmonisation (ICH) Guidelines and/or local regulatory requirements, as applicable. In addition, BeiGene or authorized designee will be responsible for the submission of safety letters to central independent ECs (IECs).

The sponsor (or authorized designee) will notify investigators of all reportable SAEs. This notification will be in the form of an expedited safety report. Upon receiving such notices, the investigator must review and retain the notice with other study-related documentation.

The investigator and IRB/EC will determine whether the informed consent requires revision. The investigator should also comply with the IRB/EC procedures for reporting any other safety information.

Suspected serious adverse reactions and other significant safety issues reported from the investigational product development program will be reported by the sponsor or its designated representative, either as expedited safety reports and/or in aggregate reports—to the relevant, competent health authorities in all concerned countries.

